**Exclusion criteria:**

- 1) Alzheimer's Disease or other neurodegenerative disease such as Parkinson's Disease;
- 2) Current use or use in the past 3 months of antimicrobial or steroid drugs;
- 3) Medical conditions affecting immune status (e.g., heart failure, inflammatory bowel disease, hepatitis C, HIV);
- 4) International travel in the past 3 months.
- 5) Previous known side effect or negative reaction to VSL#3 or *Triphala*.

Note that heart failure, inflammatory bowel disease, hepatitis C, and HIV patients are excluded due to these diseases featuring variable and significantly altered immune status and gut microbiome, which are the main outcome measures of the study. This pilot study seeks to identify relatively healthy elderly subjects to assess these markers in the context of dietary supplementation.

**Assessment visits.** Assessment personnel will be naive to the participant group assignment. Testing will take place at SOM Building 4. At T1 (baseline): participants will 1) review their study responsibilities with the opportunity to reconsider participation 2) provide a stool and small blood sample for biomarker assessment; 3) complete psychosocial measurements via questionnaires; 4) receive group assignment instructions at the end of the visit. Measures will be repeated at T2 (post-intervention period).

**Randomization.** A computer-generated randomization algorithm will determine group assignment to ensure that participant demographics are evenly distributed across study conditions.

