#### Additional Measures

Age, gender, socio-economic status, ethnic group, relationship status, education, body-mass Index and waist-hip circumference will be recorded. If for medical reasons subjects alter medications, it will be recorded via a monthly tracking form that the subject can submit.

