#### **Statistical Issues**

Analytic Approach. Summary statistics (means, SDs, ranges, frequencies) will be computed for all variables of interest and compared between the treatment arms at baseline using 2-sample tests to test if randomization achieved balance in key covariates across groups. In the event of pre-existing variable group differences associated with dependent or relevant clinical variables, the nuisance variables will be statistically controlled. Outcome measures (e.g. health-related behaviors, psychological health, and objective measures of microbiome health and inflammation) will be transformed as needed to better approximate Gaussian distributions. The proposed study period is 2 months; hence we anticipate little loss-to-follow-up. However, subjects may drop out for a variety of reasons. It is important to take missing data into account when testing hypotheses of interest. Mixed-models can be applied even if some observations are missing as long as the data are "missing at random". Missing data (e.g., drop-outs) will be tested to determine if it is informative, and the methods to test for completely random dropouts will be applied. If needed, pattern-mixture models will be developed which take "missingness" into account when estimating parameters of interest using the methods of Park & Lee.

Analysis Plan. Two sample *t*-tests will be used to compare change scores (post-treatment minus pretreatment) in each outcome. Given the multiple outcomes, we will also use O'Brien's test which can be used to compare multiple endpoints across groups; we will apply O'Brien's test to the multiple outcomes for each hypothesis (e.g., psychological health via positive and negative affect, depressive symptoms; health behaviors via diet, physical activity, medication adherence, and alcohol usage). The O'Brien test statistic is a weighted linear combination of the *t*-statistics for each outcome. Finally, we will fit mixed effects models, with a subject-specific intercept included to allow for individual variability in outcome. Main covariate effects will be treatment group, time (pre-treatment and immediately post-treatment), and the group X time interaction. Likelihood ratio tests will be used to test the significance of these covariates. A significant group X time interaction will indicate that outcome trajectories differ across treatment groups.

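### The demographics that randomisation is meant to balance are unnamed and pre-specified in no outcome analysis; they are adjusted for only after an observed baseline difference

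*Combined protocol and SAP*

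**What the plan says.** Section 9, Randomization paragraph: "A computer-generated randomization algorithm will determine group assignment to ensure that participant demographics are evenly distributed across study conditions". No balancing factor is named. Nor does the text say whether the method is stratification, minimisation or something else.

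Section 9, Additional Measures, lists what could serve as factors: "Age, gender, socio-economic status, ethnic group, relationship status, education, body-mass Index and waist-hip circumference will be recorded".

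Section 9, Statistical Issues, plans three outcome analyses:
- Two-sample t-tests that "will be used to compare change scores (post-treatment minus pretreatment) in each outcome".
- O'Brien's test, built from those same t-statistics: "The O'Brien test statistic is a weighted linear combination of the" single-outcome t-statistics.
- A mixed model "with a subject-specific intercept included to allow for individual variability in outcome", of which the plan says: "Main covariate effects will be treatment group, time (pre-treatment and immediately post-treatment), and the group X time interaction".

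The same section compares the arms at baseline "using 2-sample tests to test if randomization achieved balance in key covariates across groups", and then says: "In the event of pre-existing variable group differences associated with dependent or relevant clinical variables, the nuisance variables will be statistically controlled".

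**The concern.** When allocation forces arms to be alike on a factor that predicts the outcome, that factor no longer adds to the sampling error of the treatment difference. An analysis that leaves it out still counts its variance in the standard error. The test is then conservative, and precision already created by the design goes unused.

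The plan's one route to adjustment does not close the gap. It opens only when groups are seen to differ, and balancing makes that unlikely for these very factors. It also lets baseline tests choose the covariates, so the final model is not fixed before the data are seen.

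The stakes are power in a trial that plans 20 completers per arm, using variables that will be collected anyway. False positives and bias are not at stake.

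**Working it through.** **Inputs.** From Section 9 (Sample Size and Power) and Section 10: 60 completers, 20 in each of 3 groups; d = 0.75; two-sided alpha 0.05; 75 recruited with 20% dropout. Not in the documents: R², the share of the variance of the *change score* that the balancing factors explain. It is assumed over a range.

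**Step 1. The plan's own figure.** The plan states 80% power. For 20 v 20:
- 0.75/√(2/20) = 2.372, and 2.372 − 1.960 = 0.412, so power is 66.0% (normal) or 63.7% (noncentral t).
- 80% is reached only with about 28 to 29 per arm; 30 v 30 gives 82.8% (normal) or 81.5% (t).

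That shortfall is a separate matter. Here it sets the starting power at about 64%.

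**Step 2. Effect of omitting factors that allocation has balanced.**
- Reported SE / true SE = 1/√(1 − R²)
- Actual alpha of the unadjusted test = 2[1 − Φ(1.96/√(1 − R²))]

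For R² = 10%: 1/√0.90 = 1.054, and 2[1 − Φ(2.066)] = 0.039.

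Power at d = 0.75 was simulated with 40,000 replicates: 20 v 20, two exactly balanced binary factors, and both analyses using only the two arms compared.

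| Assumed R² | SE overstated by | Actual alpha, unadjusted | Power unadjusted | Power adjusted | Points lost |
|---|---|---|---|---|---|
| 0 | 0% | 5.0% | 63.8% | 63.7% | about 0 |
| 5% | 2.6% | 4.4% | 64.2% | 65.9% | 1.7 |
| 10% | 5.4% | 3.9% | 64.5% | 68.3% | 3.8 |
| 20% | 11.8% | 2.8% | 65.0% | 73.3% | 8.3 |

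A three-arm simulation (4,000 trials, 60 analysed, minimisation on three binary factors with assignment probability 0.85) gave gains of 2.3, 3.8 and 8.4 points at R² of 5%, 10% and 20%, measured against an unadjusted model that also pools variance over three arms. A further run at 10% gave 67% against 69%, so these gains are good to a point or two. Pooling must be held equal: by itself it lifts power from 63.7% to 64.5%, which is no credit to adjustment.

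**Step 3. Dropout.** At R² = 10%, the unadjusted alpha was 3.7% when 60 were minimised and all analysed, and 4.5% when 75 were minimised and 15 dropped out at random (3,000 trials, simulation error about 0.4 points each). Dropout loosens balance, so conservatism shrinks. The direction is as expected; the size is rough.

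**Step 4. Simple allocation.** The unadjusted SE is then valid. In simulation, adjustment still gained nothing at R² = 5%, about 2 points at 10% and about 8 at 20%.

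**Step 5. The mixed model.** With two visits and a subject intercept, a demographic effect that is constant over time cancels from group × time. In a simulated complete-data example, adding a demographic main effect left the interaction estimate (0.695) and its SE (0.348) unchanged. Only a factor × time term can gain precision.

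**Step 6. Cost of useless covariates.** Residual degrees of freedom are 60 − 3 = 57. With k covariates that predict nothing and allocation that does not balance them, intervals widen on average by about √(56/(56 − k)):
- k = 3: √(56/53) = 1.028
- k = 10: √(56/46) = 1.103
- k = 12: √(56/44) = 1.128

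Factors that are well balanced cost less; in the R² = 0 row the change is 0.1 point.

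**The case against.** A reader might infer that the standard errors are certainly too wide, that power is certainly given away, and that demographics can never enter the analysis. The documents support none of these.

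- *Allocation may not be restricted.* The plan states an aim, not a method. Simple randomisation cannot guarantee evenness with 60 to 75 people in three arms, so restriction is the natural reading, but it is not established. This stands.
- *R² may be near zero.* What counts is how well demographics predict change over 8 weeks. Stable effects on level are already differenced out, and no R² is given. At R² = 2% the loss is about 0.5 points (64.1% against 64.6%). This stands, and it is why the size is given as a range.
- *Adjustment is planned.* It is, conditionally. This corrects any claim that demographics are excluded, but the condition is least likely to be met for balanced factors.
- *Simply adding demographics to every model would not work.* Correct for group × time (Step 5), and adding every recorded demographic could widen intervals by 10% to 13%. Both points limit the form of the fix.
- *The error is on the safe side, in a pilot.* True, and it lowers the urgency. With pairwise power near 64%, a cheap gain in precision is still worth having.

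**Conclusion.** The concern holds in a conditional form. It is certain that the balancing factors are unnamed, that no outcome analysis pre-specifies them, and that adjustment waits on an observed imbalance. The consequence rests on two things the documents do not give.

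If allocation is restricted and the factors predict change, the unadjusted tests run at an alpha of about 4.4%, 3.9% and 2.8%, and lose about 2, 4 and 8 points of power, for R² of 5%, 10% and 20%; dropout makes them somewhat less conservative. If R² is zero, nothing is lost. If allocation is simple, the standard errors are correct and the issue is only unused precision. In no case are false positives inflated. This is a worthwhile improvement to specification and efficiency; it does not invalidate the planned tests.

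**What to change.** - **Randomization paragraph:** name the allocation method and the few demographic factors the algorithm uses.
- **Statistical Issues, t-tests and O'Brien's test:** replace the unadjusted t-tests by one linear model per outcome, on change or as ANCOVA, with arm and those factors as covariates. Take the pairwise contrasts from it, and feed its t-statistics to O'Brien's test.
- **Statistical Issues, mixed model:** enter the same factors with their factor × time terms, since main effects alone leave the group × time test unchanged.
- **Selection rule:** include these factors whatever the baseline comparison shows, and stop using baseline tests to select them.

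No new data are needed and the change is a few sentences of analysis wording. The price is a few degrees of freedom: about 3% wider intervals for three binary factors that predict nothing, but about 10% to 13% if 10 to 12 degrees of freedom are spent. So keep to the factors used in allocation, not every demographic recorded.

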**Measures of gut microbiome and treatments received.**

**Treatments:** Two grams of organic *Triphala* powder (Banyan Botanicals, Inc.) alone or with 1 capsule VSL#3® (VSL Pharmaceuticals, Inc.) probiotic taken with a few ounces of room temperature water in the morning and at bedtime, or placebo capsule taken morning and evening. Participants will be provided their synbiotic or placebo capsules during the T1 session. VSL#3® is a clinically validated probiotic that is commonly prescribed by UCSD GI physicians to help restore gut microflora.

**Gut microbiome assessment:** Participants will be mailed a stool collection kit prior to T1 and asked to bring their morning stool sample during the T1 and T2 assessment sessions.

**Blood marker assessment:** Participants will donate 1 vial of blood during the T1 and T2 assessments with the licensed phlebotomist.

**Experimental Conditions:**

Interested patients will provide informed consent and then be randomized to participate in the synbiotic, *Triphala* alone, or placebo alone group. Subjects will receive stool kits and a set of questionnaires to fill out at T1. Subjects will bring their morning stool sample and fill out the questionnaires again at T2.

Synbiotic Group. Subjects will be provided both written and verbal instructions and given a kit containing encapsulated Organic *Triphala* powder (Banyan Botanicals, Inc.) and VSL#3® (VSL Pharmaceuticals, Inc.) capsules. Subjects will take 2 grams of encapsulated organic *Triphala* powder and 1 capsule of VSL#3 with room temperature water in the morning and at bedtime.

Herb Only Group. Subjects will be provided both written and verbal instructions and given a kit containing encapsulated Organic *Triphala* powder (Banyan Botanicals, Inc.). Subjects will take 2 grams of organic *Triphala* powder with a few ounces of room temperature water in the morning and at bedtime.

Placebo Group. Subjects will be provided both written and verbal instructions and given a kit containing placebo capsules. Subjects will be instructed to take 2 (inert) capsules with room temperature water in the morning and at bedtime.

## **Assessment Outcomes**

Outcomes Hypothesis: Feasibility, treatment expectancy/satisfaction, retention, and adherence.

Recruitment rates will be recorded and new recruitment strategies will be formulated to overcome barriers presented by decliners for a future study. Treatment expectancy and satisfaction - 6 item credibility/expectancy questionnaire (CEQ) will be utilized. Retention (% of drop-outs) will be recorded, and exit interviews will be administered to determine reasons for drop-out. Adherence to intervention will be derived from T1 and T2 presence.

Outcomes Hypothesis: Objective measures of gut microbiome health.

*16S rDNA Sequencing:* Stool samples will be analyzed to identify alterations in the gut microbiota community structure by 16S rDNA sequencing. This experimental design will allow us to assess the efficacy of *Triphala* and probiotic species to positively modulate inflammaging and immunosenescence. We will also assess a panel of 30 cytokine/chemokines/lymphokines for this purpose. Finally, our study design permits us to evaluate potential synergistic interactions between the probiotic species and *Triphala*.

Outcomes Hypothesis: Objective measures of inflammatory status.

*Blood pressure (BP):* 3 resting automated BPs will be taken (Dinamap 1846SX) and averaged.

*Biomarkers:* Blood samples will be obtained by a licensed phlebotomist from a mobile phlebotomy service, Veni-Express in SOM Building 4's Clinical Rooms. Serum heparin or EDTA-preserved plasma will be stored at -80° C until assay in [name] laboratory space MTF-418. Inflammatory biomarkers will be assessed by ELISA (MSD, Minneapolis, MN).

For those participants who specifically consent to tissue banking in the ICF, their samples will remain in storage in [name] laboratory space MTF-418 after the end of this study. These blood and stool samples will remain under the sole control of the PI and may be investigated later for other inflammation-related biomarkers and gut microbes.

Exploratory Outcomes Hypothesis: Health-related behaviors.

*Pittsburgh Sleep Quality Index (PSQI):* A self-report of sleep quality and disturbances over a 1-month period.

Nineteen items generate seven "component" scores. The sum of scores yields one global score;

*Fruit/Vegetable/Fiber Screen and Fat Screen:* Rapid screeners with high correlations for total fat, saturated fat, cholesterol, fruit/vegetable intake.

*Leisure Time Exercise Questionnaire (LTEQ):* By Godin and Shephard, a valid and reliable self-administered questionnaire designed to measure an individual's regular physical activity level.

*Alcohol Use Disorders Identification Test (AUDIT):* A simple screening method to assess alcohol use.

Exploratory Outcomes Hypothesis: Psychological health.

*Beck Depression Scale (BDI)-II:* A 21-item self-report scale used to measure depression symptom changes.

*Perceived Stress Scale (PSS):* Assesses unpredictability, uncontrollability, and overwork/stress.

*Perceived Benefits Scale (PBS):* Yields subscales of enhanced self-efficacy, increased community closeness, increased compassion, increased faith, lifestyle changes, enhanced family closeness, and material gain.

*Positive and Negative Affect Schedule (PANAS):* Two 10 item scales of positive and negative emotionality.

*Satisfaction with Life Scale (SWLS):* Assesses satisfaction with life as a whole and has high internal consistency and temporal reliability.

*The Mindful Eating Questionnaire (MEQ):* Measures five constructs related to mindfulness of eating behavior:

disinhibition (inability to stop eating when full); external cues (eating in response to environmental cues); emotional eating (eating in response to emotional state); awareness (being aware and appreciative of effects of food on senses) and distraction (focus on other activities while eating) with 28 items scored on a 4 point scale - "Never/Rarely," "Sometimes," "Often," and "Usually/Always." This instrument has a good internal consistency reliability (Cronbach's alpha = 0.64), and construct validity.

**Ayurvedic Health Forms (AHF):** The Chopra Center's 102-item Mind/Body Quiz is used to assess body and mind constitution and state of imbalance in Clinical Ayurveda on a 3-point scale – "Never", "Occasionally", "Very often." The *Ojas/Ama* Quiz is a 20-item assessment of Yes/No questions to determine level of *Ojas* and *Ama*, which are Ayurvedic Medical classifications of immune strength and toxic burden.

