Sample Size and Power. We hypothesized a Cohen's *d* effect-size (standardized mean difference between groups) of 0.75 based on previous studies. With at least 60 subjects completing 2 visits, we will have 80% power (2-sided alpha=0.05) to detect a 0.75 effect-size (Cohen's *d*). To be conservative, we aim to recruit 75 subjects to this study, allowing for a 20% drop-out/loss-to-follow-up rate and a total of 60 subjects completing the 2 visits. Note that our calculations did not control the Type I error for the multiple endpoints. Our objective in this small pilot study is to obtain early evidence of the putative efficacy of this novel intervention on a multitude of outcomes, psychosocial and biological, in the elderly. We expect our findings to inform the design of a larger future clinical trial in elderly subjects.

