**11. RECRUITMENT AND PROCEDURES PREPARATORY TO RESEARCH**

**Overview.** A total of 75 participants who are generally healthy and otherwise meet our study criteria will be recruited and randomly assigned to either an 8-week synbiotic group, herb alone, or placebo control with a goal to obtain 60 patients who complete the study (20 in each group) after an estimated 20% attrition. Placebo control subjects will be given the option of having the 8-weeks of herbal synbiotic for directed personal use upon conclusion of the study. [name] has volunteered to help identify individuals who meet criteria for this study. Additional staff members responsible for assisting with recruitment are listed elsewhere in this application.

With this application, we are requesting a Waiver of Documented Consent to conduct the telephone screens. Asking interested individuals whether they meet the basic study criteria over the telephone (age, immune disorder diagnosis, medication use) presents no more than minimal risk of harm and involves no procedures for which written consent is normally required outside of the research context. Written consent will be obtained at the initial, in-person visit before any study questionnaires are administered or research procedures are performed.

With this application, we are also requesting a partial waiver of HIPAA authorization so that our study staff may help clinical staff identify potentially eligible participants using EPIC. When a member of our research team identifies a patient who may be eligible, he or she will then send a secure EPIC email asking the provider if they agree that a given patient is a good candidate for the study and asking the provider to speak with his or her patient about our study. The provider will provide a brief overview of the study during the patient's clinical

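### Adherence is derived from attending T1 and T2, so it appears to repeat retention and cannot show how much study product completers took

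*Combined protocol and SAP*

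**What the plan says.** Section 9, Assessment Outcomes, names retention and adherence side by side as feasibility outcomes. For retention: "Retention (% of drop-outs) will be recorded, and exit interviews will be administered to determine reasons for drop-out". For adherence: "Adherence to intervention will be derived from T1 and T2 presence".

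The same section, under Measures of gut microbiome and treatments received, says when product is issued: "Participants will be provided their synbiotic or placebo capsules during the T1 session". Product is then taken at home twice a day for 8 weeks (Sections 6 and 9).

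Drop-out is not formally defined. The sample-size paragraph links it to attendance, "allowing for a 20% drop-out/loss-to-follow-up rate and a total of 60 subjects completing the 2 visits", and Section 11 repeats the target: "with a goal to obtain 60 patients who complete the study (20 in each group) after an estimated 20% attrition". The sample-size paragraph also gives the purpose of the pilot: "We expect our findings to inform the design of a larger future clinical trial in elderly subjects".

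The Analysis Plan under Statistical Issues lists medication adherence among the health behaviours to be combined in O'Brien's test. It names no instrument or data source for it.

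**The concern.** Attendance and intake are different quantities. A participant can keep both appointments and take little product. Because the attendance rule is the stated definition of adherence, the trial would report a figure under that name that carries no information on dosing in those who stay.

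Two things are at stake. First, if the groups do not differ, the investigators could not tell an ineffective product from one that was not taken, nor see whether intake differed between the two-product kit and the single-product kits. Second, whether older adults keep up twice-daily capsules for 8 weeks is a natural design input for the larger trial that this pilot is meant to inform.

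**Working it through.** **Inputs.** 75 recruited, 60 completing both visits, 20% drop-out (Section 9, Statistical Issues; Section 11). 20 completers in each of 3 groups (Sections 10 and 11). 8 weeks of product (Section 6), twice daily (Section 9, Experimental Conditions).

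**1. The plan's own figure.** 60 / (1 − 0.20) = 75. The recruitment target reproduces exactly.

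**2. What attendance can carry.** Product is handed over at T1, so everyone who receives it was present at T1 before any dose. Only T2 attendance can vary among them.

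**3. Adherence against retention.** If drop-out means not completing the two visits:
- Planned adherence = 60 / 75 = 80%.
- Planned retention = 1 − 0.20 = 80%.

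The two are the same quantity, with the same 75 − 60 = 15 participants counted as failures in each.

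**4. Range hidden among completers.** Scheduled occasions = 8 × 7 × 2 = 112. The rule observes none of them. A completer with 0/112 and one with 112/112 both score as adherent, so adherence among completers is 100% by construction.

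**5. Search for another record of intake.** Each candidate in the supplied text was checked:
- The monthly tracking form (Additional Measures) covers medications altered for medical reasons, and its submission is left to the participant.
- Exit interviews (Assessment Outcomes) cover reasons for leaving, so they do not reach completers.
- The credibility/expectancy questionnaire covers expectancy and satisfaction.
- Stool sequencing is an outcome and is nowhere described as a check on intake.
- The monthly report and adverse-event review (Section 15, Data Safety Monitoring Plan) cover health status and events.
- Medication adherence (Analysis Plan) has no instrument. If it means study product, its only stated source is visit presence, which does not vary among completers and so cannot contribute to a group comparison there. If it means other medicines, it does not bear on product intake.

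None of these records how much product was taken.

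**6. Whether a count could be made as the text stands.** A count needs a scheduled number of capsules. The Treatments paragraph says "or placebo capsule taken morning and evening", giving no number per occasion. The Placebo Group paragraph says: "Subjects will be instructed to take 2 (inert) capsules with room temperature water in the morning and at bedtime". The number of capsules that make up the 2 g *Triphala* dose is not stated. These points must be settled before a denominator exists.

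**The case against.** The strongest reply is that the Analysis Plan's mention of medication adherence shows that something beyond attendance was intended. That is plausible, and the fix should tie the two together. But an intention without an instrument does not supply data.

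A second reply is that duplication of retention is an inference. This stands. If a participant who stopped product but attended T2 were classed as a drop-out, the two measures would separate. The documents give no such definition, so the overlap is stated here as conditional on the sample-size paragraph. Even under that alternative, the adherence rule itself would still score the participant as adherent.

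A third reply is that the written and verbal instructions to participants, which are not reproduced, may mention returning or logging product. That cannot be excluded; the finding is limited to the supplied text.

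Several stronger readings are tempting and are not supported:
- *Side effects will lead completers to cut their intake.* Sections 14 and 18 mention relief on reducing or stopping product, but they also describe the effects as transient or self-resolving. They are risk statements, not evidence about intake.
- *The placebo wording makes the same count read as 100% or 50%.* This requires reading the Treatments paragraph as exactly one capsule per occasion, and it gives no number. The point is only that the wording must be reconciled.
- *The one-week delay allowed in Section 12 distorts the dosing period.* This holds only if T2 stays fixed while the start moves. The delay is offered after consent and may shift the whole schedule.
- *The trial's comparison is invalid.* It is not. Groups compared as randomised remain comparable whatever was taken. Adherence is also not one of the Specific Aims.

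**Conclusion.** The concern holds. A listed outcome is defined by a rule that does not measure it. This is a wrong rule, not merely a missing detail. On the plan's figures it returns 60/75 = 80% overall and 100% among completers, across a possible range of 0 to 112 occasions taken.

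The equality with retention assumes that drop-out means not completing the two visits. The 100% among completers follows from the rule as written and needs no such assumption. The statement that intake is unrecorded rests on the supplied text.

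The consequence is a limit on interpretation: the pilot cannot show whether intake was sustained or differed by arm. The change should be made, because product not accounted for at T2 cannot reliably be recovered later, but the primary randomised analysis does not depend on it.

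**What to change.** 1. Report T1/T2 attendance only as retention.
2. Replace the adherence rule with a returned-product count at T2: (dispensed − returned) / scheduled, by product and arm, with the schedule running from the recorded start of product to T2. Where product is not returned, use a brief intake question at T2.
3. Ask drop-outs about intake at the exit interview that is already planned, and report the number with no data by arm.
4. Have existing staff make the count and not disclose it to outcome assessors, who are meant to be unaware of group assignment.
5. Use this variable wherever the Analysis Plan's medication adherence means study product, say so there, and report it descriptively by arm alongside the primary results.
6. Before any count, reconcile the capsule wording in the Treatments and Placebo Group paragraphs and state the number of capsules per *Triphala* dose.

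**Cost.** If all 60 completers return product, there are 20 × 2 + 20 + 20 = 80 product counts at an existing visit, plus one exit-interview question, a small amount of staff time and a minor amendment. Doses, arms and sample size are unchanged. The downside is that counts can overstate intake, because missing capsules are assumed taken, and some counts will be missing. Descriptive intake data would help the reading of a null result but would not settle it.
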